3.1.2. Missing data

Subjects may have missing specific data points for a variety of causes. In general, data may be missing due to a missed visit, non-evaluability of a specific clinical measurement at its planned clinical visit or a subject's early withdrawal from study. The general procedures outlined below describe what will be done when a data point is missing.

3.1.2.1. *Imputations of missing data*

Generally, only evaluable measurements are considered for the analyses. No values are imputed for missed or non-evaluable visits. In case of primary and secondary efficacy endpoints possible specific requirements are stated in the according analysis sections.

3.1.2.2. *Partial dates*

Partially incomplete dates (day or day/month missing) will be imputed for dates related to AEs, to concomitant medication and medical history. Completely missing dates and missing years will not be imputed.

For DOB imputed dates will be used to derive the age of the patients since only month and year are captured due to regulatory reasons in some participating countries. DOB must not

have missing month information and hence, missing months will not be imputed. DOB will be imputed as described in the following table:

	Missing	Impute	Exception
DOB	Day	15	--

Dates belonging to AEs and concomitant medication will be imputed as described in the following table:

	Missing	Impute	Exception
Start date	Day	01	Date of first dose of study drug if imputed date would be prior to date of first dose of study drug
	Day/Month	01JAN	Date of first dose of study drug if imputed date would be prior to date of first dose of study drug
Stop date	Day	Last day of the month	Patient EOS date if the imputed date would be after patient EOS date
	Day/Month	31DEC	

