3.8.2. AEs and SAEs

Verbatim descriptions of AEs will be mapped to thesaurus terms (Medical Dictionary for Regulatory Activities (MedDRA) v19. 1). Only treatment-emergent AEs, hence, AEs outlined during protocol treatment period (on or after the first dose of study drug until 30 days after the last dose of study drug or until the end of study visit, whichever occurs later) or after this period, in case of deaths, serious adverse events, or other adverse events of concern deemed related to prior study drug treatment or study procedures, will be tabulated.

All AE data will be given by System Organ Class (SOC), preferred term (PT) and grade and will be summarized overall and by treatment arm. Additionally, serious AEs, deaths, AESIs (protocol defined – based on type and severity of AE or laboratory data), as well as AEs at NCI CTCAE v4.0 Grade 3 to 4 and Grade 5 and AEs leading to discontinuation, modification (i.e. reduction) or delay (i.e. interruption) of treatment will be summarized separately. Furthermore, AE data will be listed by study site, patient number, treatment arm, date of first dose of study drug, onset and resolved study day, seriousness, duration, severity, outcome and the relationship to study drug to understand the cumulative incidence as well as the time

to onset of first event when treated with GDC-0032+letrozole. The time to AE of special interest (time from first dose of study drug to first AE of special interest) will be shown graphically.

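### The start-date exception for partial AE and medication dates is unconditional, so events recorded as beginning before first dose are moved to the day of first dose and can start after they stop

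*SAP*

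**What the plan says.** Section 3.1.2.2 opens by saying which dates are completed: "Partially incomplete dates (day or day/month missing) will be imputed for dates related to AEs, to concomitant medication and medical history". Missing years are not imputed, so every imputed date has a recorded year, and a recorded month when only the day is missing.

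The operative table has a narrower scope: "Dates belonging to AEs and concomitant medication will be imputed as described in the following table". For start dates it uses day 01, or 01JAN if the month is also missing. Both rows carry the same exception: "Date of first dose of study drug if imputed date would be prior to date of first dose of study drug". For stop dates it uses the last day of the month or 31DEC. The only exception given for stop dates is an upper limit: "Patient EOS date if the imputed date would be after patient EOS date". Neither part of the table compares start with stop.

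Section 3.8.2 restricts the AE tables: "Only treatment-emergent AEs, hence, AEs outlined during protocol treatment period", with that period described as "on or after the first dose of study drug until 30 days after the last dose of study drug" or until the end-of-study visit if later, plus certain later events. The AE listing in the same section includes "onset and resolved study day, seriousness, duration". Time from first dose to the first AE of special interest is to be plotted.

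**The concern.** Moving an ambiguous start to the day of first dose is a common conservative convention. If the day is missing and the month is that of first dose, the event may have begun before or after dosing, and calling it treatment-emergent is the cautious choice.

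The SAP's exception goes further. Its only trigger is that the imputed date precedes first dose, so it also fires when the recorded month or year, or the stop date, already shows that the event began before dosing. In those cases it overwrites collected information instead of filling a gap.

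The safety outputs in 3.8.2 are at stake. Events known to be pre-treatment would enter the treatment-emergent tables, onset days would be false and durations could be negative. An AE of special interest handled this way would appear at time zero on the time-to-event plot.

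**Working it through.** The SAP gives no figure to reproduce, so the check applies the table literally to example records.

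**Inputs.** The imputation rules come from 3.1.2.2 and the opening of the treatment-emergent window from 3.8.2. First dose is assumed to be 10 March 2015, with end of study 22 weeks later. The records are invented.

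**Rules.** Imputed start = first of the recorded month, or 1 January of the recorded year; if earlier than first dose, replace it by first dose. Imputed stop = last day of the month or 31 December, not later than end of study. An AE is treatment-emergent if start ≥ first dose. Gap = start − stop; a positive gap is impossible. The last column applies the rule proposed under the fix.

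| Record | Start under SAP | Stop | Gap | Start under proposed rule |
|---|---|---|---|---|
| AE, Feb 2015, stopped 25 Feb 2015 | 10 Mar 2015 | 25 Feb 2015 | +13 days | 1 Feb 2015 |
| AE, Feb 2015, stopped Feb 2015 (day missing) | 10 Mar 2015 | 28 Feb 2015 | +10 days | 1 Feb 2015 |
| AE, Mar 2015, stopped 5 Mar 2015 | 10 Mar 2015 | 5 Mar 2015 | +5 days | 1 Mar 2015 |
| AE, Mar 2015, stopped 20 Mar 2015 | 10 Mar 2015 | 20 Mar 2015 | none | 10 Mar 2015 |
| Medication, Jan 2014, stopped 20 Jan 2015 | 10 Mar 2015 | 20 Jan 2015 | +49 days | 1 Jan 2014 |
| Medication, 2012, ongoing | 10 Mar 2015 | ongoing | none | 1 Jan 2012 |

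Three things follow.

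1. The first three AEs all ended before dosing, yet each has start = first dose and so meets the treatment-emergent condition.
2. The second record needs no complete date at all. The table's own start and stop rules, applied together, produce a start after the stop.
3. In the third record the month matches that of first dose and only the stop date shows that the event was over. A condition on month and year alone would still give 10 March, so a stop-date condition is needed as well.

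The fourth record is the ambiguous case for which the convention is meant. Both rules give the same answer there.

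**How often the recorded month alone settles the question.** This is an illustration under assumptions, not an estimate for the trial. Take AEs with onset 1 to 28 days before first dose and the day missing, with all first-dose dates in a 365-day year equally likely.

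- All of them are moved to first dose, because the first of the onset month always precedes first dose.
- If first dose falls on day d of a month (d = 1 to 28), then 29 − d of the 28 window days lie in the preceding month; for d = 29 to 31, none do.
- Per month: 28 + 27 + … + 1 = 406. Per year: 12 × 406 = 4,872.
- All combinations: 365 × 28 = 10,220.
- Share: 4,872 / 10,220 = 0.477, about 48%.

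Under these assumptions, about half of such records would be moved to first dose although the recorded month already rules that out.

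**The case against.** The strongest reply concerns reach. Complete dates are unaffected, and nothing here feeds ORR, pCR or another efficacy analysis. The AE problem arises only if events with onset in a month or year before first dose are recorded as AEs at all. That is usually settled in the protocol, which is not at hand. These points stand and limit the severity, but they do not make the rule correct.

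Section 3.8.2 also does not say in so many words that the imputed start date decides treatment-emergent status. That is an inference, though the natural one, since the period is defined by dates and the table exists to complete them.

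A reader might infer three stronger claims that the SAP does not support:

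- **That the between-arm safety comparison is biased or diluted.** The rule applies to both arms alike, and 3.8 plans summaries by arm without a between-arm safety test. It would add spurious treatment-emergent events. No directional effect, and no size of dilution, can be shown.
- **That medication analyses are distorted.** Outside 3.1.2.2, concomitant medication appears only as a category of important protocol deviation and among the listings that 3.11 says may be presented. No table of medication start or duration is planned, so the harm is a false start date in a listing.
- **That past conditions in medical history are moved to first dose.** The introductory sentence names medical history, but the table is stated to cover AEs and concomitant medication only. As written it does not touch medical history.

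**Conclusion.** The concern holds as a defect in a stated rule. The exception has no condition on the recorded month or year and no check against the stop date, and no other section limits it. Followed exactly, it yields false first-dose onsets, treatment-emergent flags for events known to precede dosing, and negative durations in the 3.8.2 outputs. For medications it yields false start dates in listings.

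Severity is minor to moderate. The number of affected records cannot be known from the SAP, the co-primary and other efficacy endpoints are untouched, and no between-arm bias is shown. The worked gaps of 5 to 49 days and the 48% share rest on assumed dates and an assumed 28-day window. They show how the rule behaves, not how large its effect was in this trial. The conclusion on AEs also assumes that the imputed start determines treatment-emergent status and that some partially dated pre-dose events are recorded as AEs.

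**What to change.** Replace the start-date exception in both rows of the 3.1.2.2 table with:

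> Impute the first-dose date only if the known month and year (or the known year when the month is missing) equal those of first dose and the known or imputed stop date is not before first dose. In all other cases impute 01 (or 01JAN) without moving it to first dose. An imputed start may not be later than the stop date.

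The second sentence also covers months and years after first dose: an AE dated April 2015 in the example keeps a start of 1 April 2015, as it does now. Truly ambiguous dates are still assigned to first dose.

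The cost is one revised table entry and one change to the date derivation, using data already collected. Any safety tables and listings already produced under the present rule would need to be rerun.

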3.1.3. Stratification errors

Stratification errors are defined as different values in the stratification factors compared between IxRS and actual patient values from the electronic case report forms (eCRF). Variables compiled in both systems are:

- Tumor Size (T1-T2 vs. T3)
- Nodal Status (Cytologically Positive vs. Radiologically or Cytologically Negative). If on ultrasound examination there is evidence of suspicious axillary lymph nodes at the baseline examination, then FNA or core biopsy is required to confirm nodal status.

As tumor size has to be measured by MRI for actual patient values in the eCRF, but may be measured by other devices for stratification in IxRS (for which information on device type is not available), there may be several stratification errors for this strata.

Stratified analyses that are intended to evaluate the treatment effect will be based on the randomized stratum (ie, from IxRS) regardless of the subject’s actual value throughout the document unless otherwise specified. Sensitivity analyses repeating the main primary and secondary analyses using the actual stratum (i.e. stratum as given in the eCRF) may be performed additionally. If assumptions or data structure do not allow for stratified analyses, appropriate non-stratified analyses (e.g. Fisher’s exact test) will be performed. Covariate analyses where covariates are stratification factors should be based on subject’s actual value.

3.1.4. Derived endpoints

EOS visit: The date of end of study visit of each patient is defined as the maximum date of all dates during the post-surgery visit for patients who ended the study per protocol and it is the date of early EOS for patients who ended the study due to other reasons. Early EOS occurs

when a patient does not undergo surgery and/or post-surgery visit (independent of the treatment visits).

Early end of treatment (EOT): Early discontinuation from treatment occurs when a patient does not take more than 90% of investigational product (IP; =14.5 weeks=72days of dosing).

Age: Age will be calculated as the time from imputed DOB to date of randomization based on eCRF information.

PEPI score: The PEPI score will be calculated (for relapse-free survival and breast cancer-specific survival) on the basis of pathological tumor size (locally assessed – as ypTStage), node status (locally assessed – as ypNStage), Ki67 level (centrally assessed - VHIO: variable Ki67ResN), and ER status (centrally assessed - VHIO: variable ERResN, Allred score) according to Ellis et al (2008).

Tumor overall ORR assessed by modified RECIST 1.1 criteria:

Lesions should be evaluated and documented at all assessments (even if they have disappeared – laterality and location for the lesion will be set to ‘not available’). Documentation should be done at all subsequent visits for the modality where it was detected. For each modality, subject response is always relative to screening (baseline assessment) of that modality. Subject overall response per modified RECIST 1.1 criteria is assessed only at Week 16. Assessments of disease at visits prior to Week 16 visit are to rule out progression.

Target and non-target lesions are identified at screening, while new lesions are only identified after screening. If a new finding is equivocal on a particular modality, and not deemed suspicious enough to warrant clinical follow-up it should not be documented as a new lesion on that modality. Lymph nodes may be identified as non-target lesions at screening or as new lesions at another visit. Lymph nodes are not expected to disappear; a complete response (CR) may be documented if the lymph node becomes completely non-pathologic in appearance (~equivalent to non-lymph node lesion disappearing).

If a target lesion was present at screening the response at Week 16 should be documented as given in Table 1 in [Appendix 1](#) ~~Appendix 1~~.

If no target lesion was present at screening (but documented as a non-target lesion) the response at Week 16 should be documented as follows:

Non-Target Lesions	New Lesions	Overall Response
CR	No	CR
Non-CR/non-PD	No	SD (non-CR/non-PD)
Not measurable/Not assessed	No	NE
PD (Unequivocal)	Yes or no	PD
Any	Yes	PD

The latter case should not occur on MRI assessments since a measurable lesion is required for study entry, but it may occur on clinical breast examination, mammography, and/or breast U/S assessments. An overall response of PR is not possible per RECIST 1.1 if only non-target lesions are documented at screening.

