2.1.3. Safety objectives

The safety objective for this study is to evaluate the safety of letrozole plus GDC-0032 versus letrozole plus placebo.

The safety and tolerability of GDC-0032 will be assessed using the following safety outcome measures:

- Incidence, nature, and severity of adverse events (AEs) graded according to National Cancer Institute Common Terminology Criteria for AEs (NCI CTCAE), v4.0
- Incidence and type of AEs leading to dose discontinuation, modification, or delay
- Serious adverse events (SAEs)
- Protocol-defined AEs of special interest (AESI)
- Clinically significant changes in vital signs and in clinical laboratory results during the AE reporting period

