2.2.1. Surgery

Surgery will take place after at least 16 weeks of treatment, during Weeks 17 – 18. Surgery should be performed within 4 days after the last dose of GDC-0032, if possible, to best observe pharmacodynamic knockdown with GDC-0032 in the surgical specimen. Surgery may be delayed due to toxicity or other safety issues. A maximum of 16 weeks of GDC-0032 can be administered. Letrozole can be continued up to surgery by investigators decision. Information on the type of surgery will be collected and recorded. Surgery specimens will be collected for histological examination to assess for pathologic complete response (pCR) and

for other endpoint analyses. The co-primary efficacy endpoint of the primary objective, i.e. pCR (ypT0/is, ypN0), will be established via a local review following completion of neoadjuvant therapy and surgery.

An Independent Review Facility (IRF) will be used to determine the tumor ORR via MRI. IRF procedures are detailed in the IRF charter.

A post-surgery visit will be performed 4 weeks (+ 1 week) after surgery, and will mark the end of the study. Assessment of AEs and general safety will be collected at this visit.

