3.3.2. Per-protocol population

Sensitivity analyses will be based on the Per-Protocol (PP) population; that is, all patients who were randomized, received study drug (GDC-0032 or placebo), received more than 90% and less than 110% of the per protocol intake of GDC-0032 and who do not have any protocol violations that mandate their exclusion from the PP population. Hence, patients with Important Protocol Deviations (IPDs) that are expected to impact the primary endpoint of the study will be excluded (compare Study GO28888 (LORELEI)_Note-to-File_02-Feb-2016-

Signed.pdf): [ipd-DO01], [ipd-IN04n], [ipd-PE02n], [ipd-EX01], [ipd-EX02], [ipd-EX05], [ipd-EX06], [ipd-EX07], [ipd-EX12], [ipd-EX13], [ipd-EX20] and [ipd-EX26]. Patients will be analyzed according to the treatment actually received. Hence, randomized patients who wrongly received active drug at any time point will be included in the experimental arm in the PP population.

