3.5.4. Treatment disposition and exposure to study drug

Patient disposition and early discontinuation from treatment (GDC-0032/Placebo as well as letrozole) including reasons for discontinuation will be summarized by treatment arm.

Study medication intake including dose interruptions and dose reductions will be summarized overall and per treatment arm.

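### SAP 3.1.4 defines early discontinuation from treatment by cumulative intake, so the disposition summary can count patients who interrupted and resumed as discontinued and miss late permanent stops.

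*SAP*

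**What the plan says.** Section 3.1.4, under early end of treatment, gives the only definition: "Early discontinuation from treatment occurs when a patient does not take more than 90% of investigational product". A parenthesis converts the cut into time and doses: "IP; =14.5 weeks=72days of dosing". It does not refer to a permanent stop, a last-dose date or a recorded decision to stop. Early end of study, defined in the same section, rests on events: no surgery and/or no post-surgery visit.

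Section 3.5.4 uses the variable: "Patient disposition and early discontinuation from treatment (GDC-0032/Placebo as well as letrozole) including reasons for discontinuation will be summarized by treatment arm". Its next sentence treats interruptions as a different matter: "Study medication intake including dose interruptions and dose reductions will be summarized overall and per treatment arm".

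Three other places bear on the point:
- Section 2.2.1 limits the duration of the investigational drug: "A maximum of 16 weeks of GDC-0032 can be administered".
- Section 3.3.2 uses the same lower limit as an adherence condition for the per-protocol population: "received more than 90% and less than 110% of the per protocol intake of GDC-0032".
- Section 2.1.3 lists among the safety measures "Incidence and type of AEs leading to dose discontinuation, modification, or delay", and section 3.8.2 keeps these categories apart: "AEs leading to discontinuation, modification (i.e. reduction) or delay (i.e. interruption) of treatment will be summarized separately".

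**The concern.** Discontinuation normally means that a patient stopped a drug for good before the planned end, on a date and for a reason. The SAP tabulates it by arm with reasons, so readers will take the table in that sense. A rule based on total intake answers a different question, namely how much of the course was taken. The two differ in two groups: patients who lost many doses to interruptions but were back on drug at the end, and patients who stopped for good close to the end.

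The table is a between-arm tolerability summary in a trial with safety as a stated objective. If long interruptions or late stops are more frequent in one arm, the difference in discontinuation rates will partly reflect the definition. A patient who resumed has no permanent stop to which a reason could belong. A patient who stopped late because of an adverse event could appear in the adverse event table of section 3.8.2 but not in the disposition table.

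**Working it through.** **Inputs**
- Cut: intake of 90% or less of investigational product, given as 14.5 weeks or 72 dosing days (SAP 3.1.4).
- Maximum duration of GDC-0032: 16 weeks (SAP 2.2.1).
- Dosing days per week: not stated in the SAP text and therefore an assumption. It is inferred below, and 7 per week is shown as the other end of the range.
- About 330 patients, randomised 1:1 (SAP 2.2 and 2.3).

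**Step 1. Reproduce the plan's figure.**
- 0.9 × 16 weeks = 14.4 weeks; the SAP gives 14.5.
- 72 / 14.4 = 5.0 dosing days per week.
- 16 × 5 = 80 planned doses, and 0.9 × 80 = 72 exactly.
- At 7 dosing days per week, 16 × 7 = 112 and 0.9 × 112 = 100.8, so 72 would not be reproduced.

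The 72-day figure is therefore 90% of the course on a 5-day count.

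**Step 2. Apply the rule as written.** A patient escapes the flag only with more than 72 doses, that is, 73 or more of 80.

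| Dosing days per week | Planned doses | Doses needed to escape the flag | Missed doses that trigger it | Doses left at the earliest unflagged permanent stop |
|---|---|---|---|---|
| 5 (implied by the SAP) | 80 | 73 | 8 or more | 7 |
| 7 (for comparison) | 112 | 101 | 12 or more | 11 |

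**Step 3. Two patients on the 80-dose count.**
- Patient A misses 8 doses through interruptions, resumes and takes the last planned dose. Intake is 72/80 = 90%, which is not more than 90%. She is counted as an early discontinuation.
- Patient B stops permanently after dose 73. Fourteen weeks give 14 × 5 = 70 doses, so this is the third dosing day of Week 15. Intake is 73/80 = 91.25%. She is not counted. The same holds for a stop after any dose from 73 to 79, with 7 down to 1 doses left.

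Under a permanent-stop definition both classifications reverse.

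**Step 4. Effect on the table.** In one arm, let *a* be the number of patients like A and *b* the number like B. The rule's count minus the permanent-stop count is *a* − *b*. With 330 / 2 = 165 patients per arm, the arm's rate shifts by (*a* − *b*) / 165, and one patient counts for 1/165 = 0.6 percentage points. The between-arm difference is distorted by the difference of the two shifts. The SAP gives neither *a* nor *b*.

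**Step 5. Who has a rule.** Section 3.5.4 reports early discontinuation for letrozole as well, while section 3.1.4 words the rule for investigational product only. No rule for letrozole is given.

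**The case against.** The strongest reply is that the cut can be read as time on treatment: the entry concerns end of treatment, and the parenthesis gives 14.5 weeks. On that reading patient A is not counted, and the interruption half of the point falls away. The reference to taking product and to days of dosing favours intake, but the wording does leave room. The late-stop half stands on either reading: a permanent stop in the last 16 − 14.5 = 1.5 weeks is still missed.

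A second reply is that section 3.5.4 summarises interruptions and reductions in their own right. This is true, but it does not take the interrupted patient out of the discontinuation count.

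A third is that an all-cause disposition count and a count attributed to adverse events differ by design. That is right. A disagreement for particular patients is possible, not certain.

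Some stronger readings are tempting but not supported:
- A reader might infer that the SAP merges discontinuation and delay as safety outcomes. Section 3.8.2 keeps them apart and does not invoke the intake rule.
- A reader might infer that every interruption counts as discontinuation, or that late stops are reported as completed. Only a cumulative loss of at least 10% of doses triggers the flag, and the SAP does not define completion.
- A reader might hold that 14.5 weeks and 72 days contradict each other. 14.5 × 5 = 72.5, so the gap is rounding of 14.4.
- A reader might carry the 72 days over to letrozole and call the cut too low there. The SAP never applies that figure to letrozole; it simply gives no rule for it.
- A reader might want a percentage by which discontinuation is overstated. Any such figure would only restate an assumed frequency of long interruptions.

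**Conclusion.** The point holds for the disposition summary. As written, the rule counts as discontinued a patient who loses at least 10% of doses and resumes (8 or more of 80), and leaves out permanent stops with 1 to 7 of 80 doses remaining. The 80-dose count assumes 5 dosing days per week, implied by the SAP's own 72. At 7 per week the limits become 12 or more missed and up to 11 remaining, so the flaw does not depend on the schedule. The interruption error also assumes the intake reading; the late-stop error does not.

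Each misclassified patient moves an arm's rate by about 0.6 points. The net direction in either arm is unknown, because the two errors work in opposite directions.

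A reader might infer that efficacy results are at risk. They are not: the primary analysis is by intention to treat, its non-responder rule in section 3.6.2 rests on early study termination and non-evaluable MRI, and the per-protocol population carries its own intake condition. The adverse event tables are not affected either. The damage is confined to one descriptive between-arm summary and its consistency with section 3.8.2. It is worth correcting because that summary bears on tolerability and the repair is small.

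**What to change.** In section 3.1.4, define early end of treatment as a recorded permanent stop before the planned end of treatment, with its date and reason. Derive it separately for GDC-0032/placebo and for letrozole, and state the planned end used for each. Keep the 90% cut, renamed as an exposure measure, and report the share of patients with intake of 90% or less beside the interruption and reduction summaries in section 3.5.4. State the number of planned dosing days behind the 72, so that the cut can be checked.

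The cost is a change of wording, one derived variable per drug and one extra line in the exposure table. The data appear to exist: section 3.5.4 plans to report reasons, section 3.11 names treatment completion among its listings, and section 5 reports time from end of treatment to surgery for GDC-0032 and for letrozole. The case report form is not at hand, so this should be confirmed.
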